### 8.2 Setting and Study Population

### 8.2.1 Study Period

The study period will be from 17 May 2018, which is the date of US FDA approval for erenumab-aooe, to 31 May 2020 (or the latest release date for the MarketScan® claims database).

### 8.2.2 Patient Eligibility

The following four new user cohorts based on available data in a claims database will be created: (1) erenumab-aooe, (2) other mAbs targeting the CGRP pathway, (3) selected SOC migraine preventive medications (anti-epileptics), and (4) onabotulinumtoxinA. The index date is defined as the date of first claim for each of these group of medications. Use of mAbs targeting the CGRP pathway based on free/discount/coupon programs is not captured in claims data, therefore in the current protocol the term "new users" for these medications refers to the first appearance of a claim for the medication in the claims database and not necessarily the first time the patient has used the medication. Because treatment guidelines recommend inadequate response or intolerance to two SOC migraine preventive medications prior to erenumab initiation, the SOC anti-epileptic preventive medication cohort and the botulinum toxin cohort will be selected from the remaining population of migraine patients after the erenumab and other CGRP mAbs cohorts have been created.

### 8.2.2.1 Inclusion Criteria

Patients must meet the following inclusion criteria:

- 1. 18-64 years of age on the index date.
- 2. One year of continuous enrollment (ie, complete medical and pharmacy coverage) prior to and including the index date, which defines the baseline period.
- 3. A diagnosis of migraine during the baseline period, based on one of the following criteria:
  - a) ≥1 inpatient claim with a diagnosis of migraine (ICD-10-CM) diagnosis code of G43.xxx).
  - b) ≥1 outpatient evaluation and management claim with a diagnosis of migraine and a specialty code of 260 (neurologist).
  - c)  $\geq 1$  claim for emergency room visit with a diagnosis of migraine.
  - d) ≥1 outpatient evaluation and management claim with a diagnosis of migraine PLUS ≥1 pharmacy fill for a migraine-specific triptan or an ergotamine class medication within 365 days of each other
  - e) ≥2 outpatient evaluation and management claims with a diagnosis of migraine between 7 and 365 days apart.
  - f) ≥2 pharmacy fills for migraine-specific triptans or ergotamine class medications between 7 and 365 days apart.

#### 8.2.2.2 Exclusion Criteria

- (1) For the new user cohorts of mAbs targeting the CGRP pathway, no use of any medication targeting the CGRP pathway (erenumab-aooe, galcanezumab-gnlm, fremanezumab-vfrm, eptinezumab-jjmr, ubrogepant, rimegepant) in the year prior to the index date.
- (2) For the SOC migraine preventive medications (anti-epileptics) new user cohort, no use of any of the migraine preventive anti-epileptics: (topiramate, valproic acid, divalproex sodium), or any medication targeting the CGRP pathway in the year prior to the index date.
- (3) For the onabotulinumtoxinA new user cohort, no use of any onabotulinumtoxinA or any medication targeting the CGRP pathway in the year prior to the index date.

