Previous prophylactic treatment options for migraine have included anti-hypertensive drugs (eg, beta blockers and calcium channel blockers), anti-depressants (eg, tricyclics [TCAs], serotonin norepinephrine reuptake inhibitors [SNRIs], and selective serotonin reuptake inhibitors [SSRIs]), anti-epileptic medications (eg, topiramate), and botulinum toxins (indicated for the prevention of chronic migraine) (American Migraine Foundation, 2019; Estemalik et al, 2013; D'Amico and Tepper, 2008). All of these medications were originally developed for diseases other than migraine, but, more recently, two different classes of drugs blocking the calcitonin gene-related peptide (CGRP) pathway have been developed specifically for migraine: small molecule CGRP receptor antagonists (gepants) and monoclonal antibodies (mAbs), which either inhibit the canonical CGRP receptor or work by binding to the CGRP ligand (Deen et al, 2017).

The following four mAbs targeting the CGRP pathway have been approved for the prevention of migraine by the United States (US) Food and Drug Administration (FDA): erenumab-aooe (Aimovig®), fremanezumab-vfrm (Ajovy®), galcanezumab-gnlm (Emgality®), and eptinezumab-jjmr (Vyepti™). Erenumab-aooe was approved by the US FDA on 17 May 2018, followed by fremanezumab-vfrm on 14 September 2018,

galcanezumab-gnlm on 27 September 2018, and eptinezumab-jjmr on 21 February 2020.

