#### 8.2.4 Baseline Period

The index date for all medication cohorts is the earliest prescription claim date for a given medication occurring during the study period that satisfies the inclusion/exclusion criteria. The 365 days of continuous enrollment (ie, complete medical and pharmacy coverage) prior to and including the index date will be the baseline period.

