#### 8.5 Study Size

Based on recent analyses (Amgen Study 20200218) to evaluate the rate of hypertension in migraine patients, the following number of patients with a migraine preventive treatment were identified within the Marketscan® Early View claims database from May 2018 through January 2020:

- 15212 erenumab-aooe users
- 17239 galcanezumab-gnlm or fremanezumab-vfrm users
- 9242 onabotulinumtoxinA users

These migraine preventive treatment users were required to be 18-64 years of age, have a diagnosis for migraine based on ICD-10-CM diagnosis codes or one prescription order for a triptan/ergot in the prior 12 months, continuous enrollment in the claims database for at least 12 months prior to the index date, and no prior prescription for any medication targeting the CGRP pathway. These counts were generated before the February 2020 approval of eptinezumab-jjmr. Assuming a conservative 3-month growth rate of 15%, the expected number of new users during the study period (17 May 2018 – 31 May 2020) will be ~20 000 new users of erenumab-aooe, ~23 000 new users of other mAbs targeting the CGRP pathway, and ~13 000 new users of onabotulinumtoxinA. While new users of the SOC migraine preventive medications (anti-epileptics) were not evaluated, other analyses in the Optum electronic health record database suggest that this new user cohort will be at least as large as the erenumab-aooe new user cohort.

Table 2 provides the 95% confidence interval estimates for various potential risk estimates of the three cardiovascular outcomes (0.2%, 0.5%, 1%, 3%, 5%, 20%, and

30%) based on the projected sample size described above for erenumab-aooe, other mAbs targeting the CGRP pathway, and onabotulinumtoxinA. The risk of acute MI and stroke is expected to be relatively rare across all new user cohorts, while the risk of hypertension is expected to be common.

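### The one-year CGRP washout, with no rule keeping the two antibody cohorts apart, lets a patient with an older observed CGRP-antibody claim enter the other antibody cohort as a new user and sit in both arms of contrast 1

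*Protocol*

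**What the plan says.** - **Washout.** Protocol 8.2.2.2 (1) requires, for both CGRP-antibody cohorts, "no use of any medication targeting the CGRP pathway (erenumab-aooe, galcanezumab-gnlm, fremanezumab-vfrm, eptinezumab-jjmr, ubrogepant, rimegepant) in the year prior to the index date". The eligibility summary in the Abstract likewise limits this exclusion to the baseline period.
- **Index date.** Section 8.2.2 states: "The index date is defined as the date of first claim for each of these group of medications". Section 8.2.4 describes it as "the earliest prescription claim date for a given medication occurring during the study period that satisfies the inclusion/exclusion criteria".
- **New user.** Section 8.2.2 explains that for the CGRP antibodies the term "refers to the first appearance of a claim for the medication in the claims database".
- **Separation of cohorts.** The only such rule is in section 8.2.2. It says that the anti-epileptic and botulinum toxin cohorts "will be selected from the remaining population of migraine patients after the erenumab and other CGRP mAbs cohorts have been created". Nothing comparable separates erenumab from the other antibodies.
- **Study period.** Section 8.2.1: "The study period will be from 17 May 2018, which is the date of US FDA approval for erenumab-aooe, to 31 May 2020". The same sentence allows a different end date tied to the newest database release.
- **Follow-up.** Section 8.2.5 continues intention-to-treat follow-up through discontinuation and switching. Its switching rules censor per-protocol follow-up only.
- **Feasibility counts.** Section 8.5 sized the study on users with "no prior prescription for any medication targeting the CGRP pathway", with no time limit stated.

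**The concern.** Contrast 1 compares new users of erenumab with new users of the other CGRP antibodies. Its logic needs each arm to consist of people starting the class, and the arms to be different people. The entry rules do not secure either once more than a year has passed since launch. Someone who took erenumab and stopped can return as a new user of the comparator, although the earlier claims are in the same database. That patient comes with a treatment history that a true starter lacks. In the intention-to-treat analysis the first entry is still open, so the same later MI or stroke is an event in both arms.

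The sections also disagree about who counts as new. Section 8.2.2 points to the earliest recorded claim for the medication. Section 8.2.4 points to the earliest claim that passes the criteria, which may be a later one. The feasibility counts in section 8.5 used a stricter rule than section 8.2.2.2.

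**Working it through.** **Step 1. Can one patient satisfy both sets of entry rules?** Take a patient with erenumab claims in mid-2018, then no CGRP claim for more than 365 days, then a first galcanezumab claim. Assume the enrollment and migraine criteria are met each time.

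| Rule | Erenumab entry, 2018 | Other-mAb entry, after the gap |
|---|---|---|
| 8.2.2.2 (1), no CGRP use in prior year | met | met, because the erenumab claims are older than a year |
| 8.2.2, earliest recorded claim for the medication group | met | met, no older claim in the other-mAb group |
| 8.2.4, earliest claim that passes the criteria | met | met |
| 8.2.2, remaining-population rule | does not apply | does not apply |
| 8.2.5, switching | censors per-protocol follow-up only | does not block entry |

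For a different antibody the answer is the same under either index-date definition.

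**Step 2. When is it possible?** Section 6.1 gives the launch dates: "Erenumab-aooe was approved by the US FDA on 17 May 2018, followed by fremanezumab-vfrm on 14 September 2018", then galcanezumab on 27 September 2018 and eptinezumab on 21 February 2020. The study period of 17 May 2018 to 31 May 2020 is 746 days inclusive. The first index date at which a launch-day claim lies outside a 365-day lookback is launch + 366 days.

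| First antibody | First exposed index date | Index days to 31 May 2020 | Share of 746 |
|---|---|---|---|
| Erenumab | 18 May 2019 | 380 | 51% |
| Fremanezumab | 15 Sep 2019 | 260 | 35% |
| Galcanezumab | 28 Sep 2019 | 247 | 33% |
| Eptinezumab | 21 Feb 2021 | 0 | 0% |

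Before 18 May 2019 the one-year lookback already reaches back to launch.

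**Step 3. How many patients?** The protocol gives no persistence, switching or re-initiation figures, so this rests on assumptions:

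- entry is uniform over the study period;
- 30-50% are still on drug at 12 months (exponential persistence);
- 30-50% of stoppers later try another CGRP drug, after an exponential gap with mean 6-18 months.

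A starter counts when the gap exceeds 365 days and the second start falls before data end. Simulating 400 000 starters per scenario gives 0.3-1.2% by 31 May 2020. If a later release were used with an assumed cut at 31 December 2020, the result is 0.6-2.8%. The calculation ignores disenrollment and the need to meet the migraine criteria again. It also lets all starters enter from 17 May 2018, although the other antibodies came later. These simplifications push the figure up.

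**Step 4. How many events?** Section 8.5 projects 20 000 + 23 000 = 43 000 starters and assumes 0.60 strokes and 0.15 MIs per 100 person-years.

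- Persons: 0.003 × 43 000 = 129 to 0.012 × 43 000 = 516.
- Upper bound, giving all 516 the longest possible overlap of 380 days: 516 × 380/365.25 × 0.0060 = 3.2 strokes; × 0.0015 in place of 0.0060 = 0.8 MIs.
- With half that overlap: 1.6 strokes and 0.4 MIs.
- For scale, if each starter had one year of follow-up (an assumption): 43 000 × 0.0060 = 258 strokes and 43 000 × 0.0015 = 64.5 MIs.

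**Step 5. Per-protocol follow-up.** Section 8.2.5 places discontinuation at the end of the last days' supply plus a 60-day extension. The second entry needs more than 365 days since the last CGRP claim. Overlap would need a days' supply above 365 - 60 = 305 days, so it would normally not arise.

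**Step 6. After the change.** With a lookback over all observed claims since 17 May 2018, the index days on which an observed earlier CGRP-antibody claim can be missed fall from 380 to 0.

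**The case against.** The best defence is that a fixed 365-day window treats every patient alike. Section 8.2.2.1 requires only one year of enrollment, so a patient who joined the database after May 2018 has no older history to examine. A lookback to launch would differ by enrollment date. This stands. A reader might infer that the whole claims history is available for everyone and that the one-year limit buys nothing; the documents support neither.

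Second, sections 8.2.2, 8.9.1.1 and 8.9.4 already admit prevalent users. Section 8.9.1.1 reports that 76% of early erenumab users, and later about 60%, were covered through discount or coupon programs. That contamination may well be far larger than the one here, and the fix does not touch it. But it is use that claims cannot show. The present point concerns claims that are recorded and then disregarded, and the stated limitation does not cover people appearing in both arms.

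Third, the effect is tiny and its size rests on assumptions. This also stands. A reader might go on to infer a bias toward 1, but no risk ratio was estimated in the calculation and the protocol offers no basis for a direction.

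Fourth, re-entry on the same drug is not established. Section 8.2.4 read alone would allow it; the first-claim wording of section 8.2.2 would not. The difference from the feasibility counts also carries little weight, since section 8.5 offers its estimates for information only and those counts used a different migraine definition.

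**Conclusion.** The point holds as a gap in the cohort-entry rules. As written, a patient with an observed CGRP-antibody claim more than a year old can enter the other antibody cohort as a new user, and under intention-to-treat follow-up can be in both arms of contrast 1 at once. That conclusion follows from the text and needs no assumption about numbers.

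The consequence is minor. The number affected cannot be computed from the protocol. Under the assumptions above it is about 0.3-1.2% of starters by 31 May 2020, with at most about 3 strokes and 1 MI counted twice, so the effect on the risk ratio is probably very small. It would grow with a later data cut. The comparisons with the anti-epileptic and onabotulinumtoxinA cohorts are not at issue here, because section 8.2.2 draws those cohorts from the patients left after the CGRP cohorts are formed. This is a cheap improvement, not a threat to the study's validity.

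**What to change.** In section 8.2.2.2 (1), for the erenumab and other-mAb cohorts only, add to the one-year baseline an exclusion of any patient with an observed claim for a CGRP-pathway medication from 17 May 2018 to the day before the index date. Each patient can then enter only the cohort of the first observed CGRP antibody.

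Reconcile sections 8.2.2 and 8.2.4 to match for these two cohorts, so that a later claim cannot stand in for an ineligible first one. Leave the index date for the anti-epileptic and onabotulinumtoxinA cohorts unchanged: section 8.2.4 governs all cohorts, and tying it generally to a CGRP claim would misdefine theirs.

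The cost is wording and a short programming change, a probably small loss of patients, and a lookback whose length varies with enrollment date. Patients whose first observed claim came before they had a year of enrollment would be lost altogether. Coupon use and claims made before enrollment stay unseen.

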### 8.2.5 Study Follow-up

Follow-up will be evaluated in two ways. With an 'intention-to-treat' analysis, patients will be followed for all available time after they initiate a medication, irrespective of whether they discontinue the medication or not, or whether they switch to an alternate medication or not. Follow-up begins the day after the index date and ends at first occurrence of: (a) the outcome of interest, (b) disenrollment from a health plan, or (c) end of study period.

With a 'per-protocol analysis' patients are followed for as long as they are actively taking the medication of interest during the follow-up period. Follow-up begins the day after the index date and ends at first occurrence of: (a) the outcome of interest, (b) disenrollment from the health plan, (c) discontinuation of study medication, (d) switching to the alternate medication, or (e) administrative end of study. When a gap greater than the allowable gap of 30 days is encountered, discontinuation of study medication occurs at the end of the last prescription which includes the days supply (+60 day extension). Censoring due to switching will occur for the new user cohorts in this study when the following conditions are met:

- (1) For new users of erenumab-aooe, initiation of any other medication targeting the CGRP pathway (galcanezumab-gnlm, fremanezumab-vfrm, eptinezumab-jjmr, ubrogepant, rimegepant) during the follow-up period.
- (2) For new users of other mAbs targeting the CGRP pathway, initiation of erenumab-aooe, ubrogepant, or rimegepant during the follow-up period.
- (3) For new users of the SOC migraine preventive medications (anti-epileptics), initiation of any medication targeting the CGRP pathway (erenumab-aooe, galcanezumab-gnlm, fremanezumab-vfrm, eptinezumab-jjmr, ubrogepant, rimegepant) during the follow-up period.
- (4) For new users of onabotulinumtoxinA, initiation of any medication targeting the CGRP pathway (erenumab-aooe, galcanezumab-gnlm, fremanezumab-vfrm, eptinezumab-jjmr, ubrogepant, rimegepant) during the follow-up period.

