### Decision to Proceed to Comparative Analyses

The decision to move forward with the comparative analysis for either the acute MI or the stroke outcome will be made after assessment of covariate balance across treatment groups (eg, based on an absolute standardized mean difference of > 0.10 for covariates included in the PS model, and adequate overlap in the PS across treatment arms), null findings for the final set of negative control outcomes (ie, posterior probability > 90% that the level of bias is less than 10% of the null), and sufficient sample size to detect a risk ratio of 2.0 or greater. For the relatively rate outcome of acute MI, a total of 15,000 patients in each comparator arm will be needed in order to detect a risk ratio of 2.0 or greater, assuming 80% power and a background rate of acute MI of 0.15 per 100 person-years. In contrast, for the outcome of stroke, 3,750 patients will be required in each treatment arm to detect a risk of 2.0 or greater, assuming 80% power and a background rate of stroke of 0.60 per 100 peson-years.

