### Modeling Assumptions

Results from these analyses will be subject to limitations if certain assumptions of the methods are violated. The assumptions include the following:

- i. Conditional exchangeability, given measured covariates
- ii. No misclassification of the exposure, outcome, or other study variables
- iii. Stable unit treatment value assumption (SUTVA), which requires that outcomes are not correlated
- iv. Consistency, such that exposures can be mapped to well-defined interventions
- v. Positivity, wherein there are at least some exposed and unexposed individuals at each level of the confounders
- vi. No misspecification of the three models considered in these analyses: (a) the structural (ie, weighted) model, (b) the exposure model (ie, the PS model), and (c) the censoring model(s).

Discussion of the impact of violations of these assumptions are deferred to later sections.

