160.6	ICD-10-CM Diagnosis	Nontraumatic subarachnoid hemorrhage from other intracranial arteries	1 IP
160.7	ICD-10-CM Diagnosis	Nontraumatic subarachnoid hemorrhage from unspecified intracranial artery	1 IP
160.8	ICD-10-CM Diagnosis	Other nontraumatic subarachnoid hemorrhage	1 IP

Code	Code type	Code description	Setting (Any diagnosis position)
160.9	ICD-10-CM Diagnosis	Nontraumatic subarachnoid hemorrhage, unspecified	1 IP
l61	ICD-10-CM Diagnosis	Nontraumatic intracerebral hemorrhage	1 IP
l61.0	ICD-10-CM Diagnosis	Nontraumatic intracerebral hemorrhage in hemisphere, subcortical	1 IP
l61.1	ICD-10-CM Diagnosis	Nontraumatic intracerebral hemorrhage in hemisphere, cortical	1 IP
l61.2	ICD-10-CM Diagnosis	Nontraumatic intracerebral hemorrhage in hemisphere, unspecified	1 IP
161.3	ICD-10-CM Diagnosis	Nontraumatic intracerebral hemorrhage in brain stem	1 IP
l61.4	ICD-10-CM Diagnosis	Nontraumatic intracerebral hemorrhage in cerebellum	1 IP
l61.5	ICD-10-CM Diagnosis	Nontraumatic intracerebral hemorrhage, intraventricular	1 IP
161.6	ICD-10-CM Diagnosis	Nontraumatic intracerebral hemorrhage, multiple localized	1 IP
161.8	ICD-10-CM Diagnosis	Other nontraumatic intracerebral hemorrhage	1 IP
l61.9	ICD-10-CM Diagnosis	Nontraumatic intracerebral hemorrhage, unspecified	1 IP

	1	-		
Characteristic	Treatment Model	Censoring Model	Numerical (N) or categorical (C)	Covariate assessment period*
Demographics	Index Date			
Age (years), 18-24, 25-34, 35-44, 45-54, 55-64	Х	X	С	
Gender (male, female)				
Geographical region (eg, Midwest, Northeast, South, West)	Х	х	С	
Select Migraine Diagnoses				Baseline period
Chronic migraine (without aura)	Х	X	С	
Migraine with aura	Х	Х	С	
Acute Migraine Medications				Baseline period
Triptans	Х	Х	С	
Ergotamines	Х	Х	С	
Nonsteroidal anti- inflammatory drugs (NSAIDs)	Х	X	С	
Opioids	Х	Х	С	
Non-opioid, non-NSAID analgesics	Х	Х	С	
Gepants	Х	Х	С	
Other acute migraine-specific treatments	Х	X	С	
Non-CGRP Mediated Migraine	Preventives			Baseline period
Any MPT	Х	Х	С	
Select anti-depressants	Х	Х	С	
Select anti-epileptics	Х	Х	С	
Botulinum toxins	Х	Х	С	
Other migraine preventive agents	Х	X	С	

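### In contrasts 2 and 3 the comparator washout is not applied to the erenumab arm, so positivity fails at drug level by design, and class-coded covariates can hide it

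*Protocol*

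**What the plan says.** Section 8.2.2.2 sets a different washout for each cohort, each over the year before the index date:

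- Erenumab and the other antibodies: "For the new user cohorts of mAbs targeting the CGRP pathway, no use of any medication targeting the CGRP pathway".
- Anti-epileptic cohort (contrast 2): "no use of any of the migraine preventive anti-epileptics: (topiramate, valproic acid, divalproex sodium", and no CGRP-pathway drug.
- OnabotulinumtoxinA cohort (contrast 3): "no use of any onabotulinumtoxinA or any medication targeting the CGRP pathway in the year prior to the index date".

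Appendix D then lists "Select anti-epileptics" and "Botulinum toxins", assessed over the baseline period, for both the treatment and the censoring model. It does not say which drugs they cover. Table 1 does so for the descriptive covariates: eight anti-epileptics, of which three are washed out, and four botulinum toxins, of which one is washed out. Section 8.2.4 counts the index date as part of the baseline period.

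The modeling assumptions in Section 8.7.2.4 include "Positivity, wherein there are at least some exposed and unexposed individuals at each level of the confounders". The section defers the effect of violations to later sections, but the limitations in Section 8.9 do not return to positivity.

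The comparability text in Section 8.7.2.4 treats an absolute SMD above 0.1 as potential imbalance. The decision to proceed gives as its example of a balance assessment "based on an absolute standardized mean difference of > 0.10 for covariates included in the PS model", which is the reverse.

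**The concern.** An erenumab initiator with a topiramate, valproic acid or divalproex claim in the prior year cannot have a match in the anti-epileptic cohort, because any such patient was excluded from it. The same holds for prior onabotulinumtoxinA in contrast 3. Section 8.2.2 makes such use likely, since it cites guidance that two standard preventives should have failed before erenumab is started. Inverse probability weighting reweights patients who exist and cannot supply a missing stratum.

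Two of the three causal contrasts are affected. The negative control analyses use inverse probability weights for the same contrasts, so they inherit the problem. If the comparison goes ahead unrepaired, patients with recent experience of the comparator drug are set against patients who have been off it for at least a year.

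**Working it through.** **Inputs.** Section 8.5 projects about 20,000 erenumab users, about 13,000 onabotulinumtoxinA users, and an anti-epileptic cohort at least as large as the erenumab cohort (20,000 used here). Section 8.7.2.4 requires 15,000 per arm for acute MI and 3,750 for stroke, for a risk ratio of 2.0 at 80% power, with background rates of 0.15 and 0.60 per 100 person-years. The prevalence p of prior-year comparator-drug use in the erenumab arm is not given, so it is an assumption and a range is shown.

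**The plan's sample-size figures.** Events needed for a ratio of 2.0 (Schoenfeld, two-sided 0.05, 80% power) are 4 × (1.960 + 0.842)² / (ln 2)² = 65.3, rounded up to 66. With one year per patient, n per arm = 66 / (3 × rate): 66 / 0.0045 = 14,667 for MI and 66 / 0.018 = 3,667 for stroke. The pooled two-proportion formula gives 15,662 and 3,888. The stated 15,000 and 3,750 lie between these and are accepted.

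**Drug-specific indicator, before weighting.** With prevalence p against 0, SMD = p / √(p(1 − p)/2) = √(2p/(1 − p)). This passes 0.1 at p = 0.01/2.01 = 0.5%.

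**Drug-specific indicator, after weighting.** Prior users have propensity score 1 and weight 1. The other erenumab users have score n₀/(n₀ + N_C), where n₀ = N_E(1 − p), so their weights sum to n₀ + N_C. The weighted erenumab total is N_E + N_C, and the weighted prevalence is π = p × N_E/(N_E + N_C). That is 0.5p in contrast 2 and (20/33)p = 0.606p in contrast 3. The comparator prevalence stays 0, so SMD = √(2π/(1 − π)).

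| p (assumed) | SMD unweighted | SMD weighted, contrast 2 | SMD weighted, contrast 3 | Erenumab users without prior use |
|---|---|---|---|---|
| 1% | 0.14 | 0.10 | 0.11 | 19,800 |
| 5% | 0.32 | 0.23 | 0.25 | 19,000 |
| 10% | 0.47 | 0.32 | 0.36 | 18,000 |
| 20% | 0.71 | 0.47 | 0.53 | 16,000 |
| 40% | 1.15 | 0.71 | 0.80 | 12,000 |

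Setting π = 0.4975% gives the limiting p: 0.4975/0.5 = 1.0% in contrast 2 and 0.4975/0.606 = 0.8% in contrast 3. If the unweighted standard deviation is kept in the denominator, the values at 20% are 0.35 and 0.43, so the conclusion does not depend on that convention.

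**Class indicator (Table 1 coding).** Suppose 30% of erenumab users had a washed-out drug and a further 15% another anti-epileptic, against 15% with another anti-epileptic in the comparator. The crude class SMD is 0.30 / √((0.45 × 0.55 + 0.15 × 0.85)/2) = 0.69. Class users number 9,000 + 3,000 = 12,000 of 40,000, so weighting sets class prevalence to 30% in both arms and the class SMD to 0; comparator class users carry weight 12,000/3,000 = 4. Two-thirds of the weighted erenumab class users had a washed-out drug, which is 20% against 0%: SMD = √(0.4/0.8) = 0.71. The balance table passes and the imbalance remains.

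**Arm size under restriction.** 20,000 × (1 − p) falls below 15,000 when p > 1 − 15,000/20,000 = 25%, and below 3,750 when p > 1 − 3,750/20,000 = 81%. Against 20,000 anti-epileptic users, two-proportion power for an MI risk ratio of 2.0 is still 84% at p = 25% and 83% at 30%, and reaches 79.7% at 40%.

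**The case against.** Several points for the plan stand.

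- A reader might infer that contrasts 2 and 3 cannot satisfy the balance criterion. The documents do not support that. Under the Table 1 classes the comparator indicator is not structurally zero and can be balanced, at least in contrast 2. In contrast 3 balance would rest on however few users of the other three toxins there are.
- The 0.1 threshold is not a hard stop. Section 8.7.2.4 describes an iterative process that offers trimming and outcome-model adjustment, and Section 4 lets a contrast be dropped. However, adjusting in the outcome model for a stratum that one arm lacks is extrapolation, and trimming targets these patients only if the indicator is drug-specific.
- The larger SMDs (0.71 at p = 20%, 1.15 at 40%) are unweighted and do not measure what weighting leaves behind.
- A reader might count the lost patients as harm done by the present text. The proposed restriction loses essentially the same patients as trimming would. What differs is that the restriction is fixed and stated in advance. The MI requirement in contrast 3 is in any case already missed, with about 13,000 onabotulinumtoxinA users.
- Section 8.2.2 speaks of two standard preventives in general, not of topiramate or onabotulinumtoxinA within the past year, so it supports a non-trivial p without fixing its value.

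Two neighbouring observations add nothing to this point. Gepants are excluded at baseline in every cohort, so that Appendix D covariate is a constant with no effect. The per-protocol switching rule ("For new users of erenumab-aooe, initiation of any other medication targeting the CGRP pathway") does not censor an erenumab user who starts the comparator drug, but that is a separate design choice about the per-protocol question, not a positivity failure.

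**Conclusion.** The concern holds at drug level. The asymmetric washout leaves erenumab users with prior comparator-drug use without any possible counterpart in contrasts 2 and 3, and nothing else in the protocol repairs it. Which consequence follows depends on coding that Appendix D leaves open. With drug-specific indicators, weighting alone is enough only if p is below about 1.0% (contrast 2) or 0.8% (contrast 3); otherwise trimming redefines the population after the data are seen. With class indicators, the comparison can proceed with the violation hidden, which is the worse outcome.

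The figures rest on the projected cohort sizes and on assumed values of p. They also treat prior use of the comparator drug as the only covariate. The resulting bias in the MI or stroke risk ratio cannot be calculated from the documents. Contrast 1 and the descriptive objectives are unaffected. The reversed 0.10 criterion in the decision to proceed is a separate, plain error in the same step.

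**What to change.** 1. For contrast 2, exclude erenumab initiators with a topiramate, valproic acid or divalproex claim in the prior year. For contrast 3, exclude those with a prior-year onabotulinumtoxinA claim. Leave the erenumab cohort unchanged for contrast 1 and the descriptive analyses.
2. In Appendix D, name the drugs behind each indicator and split the classes. Remove only the washed-out drugs from that contrast's propensity model and keep the other anti-epileptics and toxins. Dropping a whole class would lose adjustment for drugs that are not washed out.
3. State that the index-date claim does not count as baseline use. Read literally, Section 8.2.4 would set the indicator to 1 for every comparator patient, which is non-positivity in the other direction.
4. State that contrasts 2 and 3 apply to patients without recent use of the comparator drug.
5. Count p before any outcome is examined, and check 20,000 × (1 − p) against 15,000 for MI (missed if p > 25%) and 3,750 for stroke (missed only if p > 81%).
6. Reword the balance criterion in the decision to proceed as an absolute SMD of not more than 0.10 after weighting.

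The cost is protocol and code wording, a smaller erenumab arm in two contrasts, and a narrower target population. For the contrast concerned, the excluded patients have no comparator to be set against.
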